2.3. Study Plan

After the parent(s) or legal guardian(s) provide informed consent (obtained up to 28 days prior to randomization), subjects will be assessed for study eligibility for Part B at the screening visit. Subjects who continue to meet eligibility criteria at baseline will undergo Day 1 baseline assessments and will be randomly assigned in a 1:1:1 ratio to REGN2222 30 mg/kg single dose (1 dose REGN2222 and 1 dose placebo), REGN2222 30 mg/kg Q8 weeks (2 doses of REGN2222), or placebo (2 doses of placebo). The study flow diagram for Part B is depicted in Figure 1.

Figure 1: Part B: 30 mg/kg IM (1 Dose REGN2222 and 1 Dose Placebo), 30 mg/kg IM (2 Doses of REGN2222), or Placebo IM (2 Doses of Placebo)

EOS = end of study; IM = intramuscular; Q8 = every 8

Note: The screening visit occurs from Day -28 to Day -1. Black arrows denote dosing visits. Subjects will be monitored on site for at least 1 hour after each dose of REGN2222 or placebo. Grey arrows denote study visits at which dosing does not occur. Visits 8, 9, and 10 will occur via phone call. In the event an AE is reported during a phone call visit, an unscheduled onsite visit may be required to follow-up, per investigator.

In Part B, assessment of the clinical efficacy endpoints will only occur during the 150 day study period (ie, through Visit 7). Any RSV infection occurring after Day 150 visit will not be included in the efficacy evaluation. If a primary endpoint is reached during the study period, ongoing assessments for other endpoints and measurements will continue until the end of the study period. Subjects who reach the primary endpoint during the study period will not have additional study drug administered for the remainder of the RSV season because the risk of a second RSV infection is substantially (~70%) reduced for 6 months after the first infection (Ohuma 2012) and this practice is consistent with recommendations in the 2014 AAP guidelines for palivizumab. Subjects who have reached the primary endpoint will continue to be monitored for additional medically attended acute respiratory infections that may occur during the study period.

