During the 150-day efficacy assessment period, data will be collected on subjects with any acute respiratory illness requiring medical attention. After enrollment of their infant into the study, parent(s) or guardian(s) taking their enrolled infant to a healthcare provider (inpatient or outpatient, including hospitalizations, ER, UC, or pediatric clinic) will be asked to contact the study staff immediately or soon after seeking medical attention for any of the following symptoms: fever, cough, earache, nasal congestion, rhinorrhea, vomiting after coughing, wheezing, or difficulty breathing (labored, rapid, or shallow).

When the parent(s) or guardian(s) takes their child for medical attention for an acute respiratory infection, they will be instructed to take a Medical Information Packet with them for the treating clinician. All infants who have a medically attended visit for a respiratory illness will be asked to have an unscheduled study visit as soon as possible or within 72 hours of discharge from the medical facility. Study site personnel will evaluate the subject during an unscheduled visit, including a history of the acute illness and nose swab collections for viral detection will occur. All nose swabs will be tested using a reverse-transcriptase polymerase chain reaction (RT-PCR) assay for RSV, which will be conducted in a central laboratory. All RSV isolates will be tested for their subtypes, specifically subtype A or subtype B. If the unscheduled study visit following a medically attended respiratory infection occurs >72 hours but <14 days of discharge from the medical facility, all procedures (as appropriate), including nose swab collection, should occur despite being outside of the 72 hour window. Unscheduled study visits for medically attended respiratory illness will be required through Day 150 even if a child has had a prior RSV-confirmed or other respiratory illness. Unscheduled study visits for medically attended respiratory illness will not be required between the day after the Day 150 visit and Day 237 (end of study) visit for the purpose of nose swab collection.

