4.6.1. Primary Efficacy Variable

The primary efficacy variable is the proportion of FAS subjects with a medically attended RSV infection (hospitalization or outpatient LRTI) during the 150-day efficacy assessment period. The 150-day efficacy assessment period is defined as the first study drug administration through the Day 150 visit (defined as the protocol specified window which includes Study Day 155). In the event that Day 150 visit occurs beyond the protocol specified window (ie, on or after Day 156) and a respiratory AE is reported at that visit, that AE will only be considered for the primary endpoint if its start date is before Study Day 156.

A medically attended RSV infection (hereafter referred to as a primary endpoint event) is defined as an infant with a positive RSV test by RT PCR with any of the following events:

- Hospitalized (on the basis of the assessment of the admitting physician) for RSV infection.
- Outpatient visit (emergency room [ER], urgent care [UC], or pediatric clinic [PC] for either a sick or well visit) with RSV LRTI.

An RSV LRTI in an infant is defined as an RSV-proven respiratory infection (ie, positive RSV RT-PCR test) with parent(s)/guardian(s) report of cough or difficulty breathing, and with 1 of the following signs of LRTI, as assessed by a healthcare provider:

- Lower chest wall indrawing
- Hypoxemia (peripheral capillary oxygen saturation $<95\%$ breathing room air)
- Wheezing or crackles

The positive RSV RT-PCR test has to occur within a 14-day period since the start date of the adverse event (AE) corresponding to the medically attended respiratory illness (MARI), ie, the specimen collection date for RT-PCR - AE start date must be ≤ 14 . If multiple medical visits are made for the same episode of RSV illness, an RSV positive test by RT-PCR at any medical visit will label that episode as being RSV positive, and it will be counted toward the primary endpoint. If there are multiple medically attended visits during an episode associated with an RSV positive test, then the most severe occurrence will be defined as the primary endpoint event, and events of decreasing severity will be defined in the following order: RSV positive hospitalization $>$ RSV positive ER/UC LRTI $>$ RSV positive pediatric clinic LRTI. If a subject had multiple episodes of RSV infection, the first episode will be defined as the primary endpoint.

[figure not shown]

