Only medically attended respiratory illness occurring during the 150-day efficacy assessment period will be considered for the primary endpoint. If categorization of a MARI event as an endpoint is unclear, source documentation will be provided to a blinded adjudication committee for categorization prior to database lock.

If an infant has a medically attended respiratory event but did not have an RT-PCR test conducted in the central laboratory within 14 days after onset of the episode of RSV illness, results from a RSV RT-PCR assay conducted in the local lab will be used to determine RSV infection if the RSV RT-PCR assay is reviewed by jurisdictional health authority and released for commercial distribution, or conducted in a laboratory that is currently certified for human diagnostic testing. To that end, protocol has specified the following conditions for acceptable local lab RSV RT-PCR assays:

- Assay is a FDA-cleared RSV RT-PCR assay or
- Assay is an RSV RT-PCR assay that is not FDA-cleared but is conducted in a laboratory that is currently CLIA (or equivalent) certified.

The algorithm to programmatically derive an observed primary endpoint event is depicted in [Figure 2](#).

Figure 2 Flow diagram to depict the programmatic derivation of an observed primary endpoint event

Answers to questions (1) through (7) in the flow diagram are collected from the following electronic case report form (eCRF) pages and other source data:

- Questions (1) and (3): eCRF page of “History of Medically-Attended Acute Respiratory Illness (MARI) Questionnaire”.
- Question (2): eCRF page of “Hospitalization for Respiratory Illness Questionnaire”.
- Question (4): eCRF page of “Lower Respiratory Infection (LRI) Questionnaire”.
- Questions (5): eCRF page of “Central Laboratory” for nose swab collection and eCRF page of “History of Medically-Attended Acute Respiratory Illness (MARI) Questionnaire” for AE start date.
- Question (6): Central lab RSV RT-PCR test results from Viracor.
- Questions (7) and (8): eCRF page of “Unscheduled RSV RT-PCR (Local Lab)”

On the eCRFs, the MARI questionnaire, the LRI questionnaire, and the central (or local) lab RSV PCR test(s) are designated by the investigator to a corresponding medically-attended acute respiratory adverse event (AE). Therefore, the corresponding AE serves as the key variable to programmatically merge information from the MARI and LRI pages with RSV PCR test(s) for each episode of illness.

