5.7.5.3. Non-RSV Medically Attended Respiratory Illness

To evaluate the effect of REGN2222 on the non-RSV MARI, the proportion of subjects who had medically attended respiratory illness (hospitalization or outpatient LRTI) not confirmed to be related to RSV (either all negative RSV or missing RSV testing results within 14 days since AE onset) will be summarized for each treatment group. If a subject had both non-RSV MARI and RSV MARI (ie, the primary endpoint event), they will not be included in the numerator when calculating the proportion. For this particular analysis, only observed events will be included as events. Treatment difference in this proportion will be summarized using descriptive statistics.

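### SAP 5.7.5.3 removes infants with an RSV event from the non-RSV illness numerator and counts untested illness as non-RSV, so the treatment difference carries a bias of unknown net direction

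*SAP*

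**What the plan says.** SAP 5.7.5.3 summarizes, by treatment group, the proportion of subjects with a hospitalization or outpatient lower respiratory tract infection (LRTI) not confirmed as RSV, and reports the treatment difference descriptively from observed events only. Two rules define the numerator.

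- Infants who also had the primary endpoint event are left out: "If a subject had both non-RSV MARI and RSV MARI (ie, the primary endpoint event), they will not be included in the numerator". Nothing removes them from the denominator. SAP 3.1 makes the full analysis set (FAS) the primary set for all efficacy endpoints.
- An illness qualifies as non-RSV on the basis of "either all negative RSV or missing RSV testing results within 14 days since AE onset".

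Other sections bear on these rules.

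- Surveillance continues after an RSV event. SAP 2.3 says "Subjects who have reached the primary endpoint will continue to be monitored for additional medically attended acute respiratory infections", and that unscheduled illness visits "will be required through Day 150 even if a child has had a prior RSV-confirmed or other respiratory illness".
- Swabs can be late. SAP 2.3 says that if the unscheduled visit "occurs >72 hours but <14 days of discharge from the medical facility, all procedures (as appropriate), including nose swab collection, should occur". SAP 4.6.1 counts a positive result only within 14 days of the adverse event (AE) start date.
- SAP 4.6.1 accepts a qualifying local RT-PCR result where there is no central test within 14 days of onset. It also says that "an RSV positive test by RT-PCR at any medical visit will label that episode as being RSV positive", and it links tests to illnesses through the AE record.
- SAP 5.12 takes its non-RSV illness definition from 5.7.5.3 for the pathogen-panel table, with FAS subjects as the denominator.

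**The concern.** The RSV event occurs after randomization and is the outcome that treatment is meant to prevent. Leaving out infants who had it removes more placebo infants than REGN2222 infants. Because follow-up continues, some of those infants will have had a genuine non-RSV illness as well. Taken alone, this makes REGN2222 look worse.

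Counting untested illness as non-RSV works the other way. Some untested illnesses are really RSV, and there are more of these on placebo simply because RSV is commoner there. Testing rates need not differ between arms. Illnesses swabbed too long after onset can fall into this group too.

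What is at stake is interpretation. A small difference, or none, would be open to misreading as evidence about non-RSV illness. SAP 8 says the first-step results will be used to plan a separate efficacy study and to communicate with health authorities.

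**Working it through.** **Inputs from the documents.** RSV event rates of 10% (placebo) and 4% (REGN2222), and about 1200 subjects in three equal arms, so 400 per arm (SAP 2.2). Section 5.7.5.3 gives no figure of its own, so I first checked the design that supplies the rates.

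- A continuity-corrected chi-square test at 2-sided 0.025 with 90% power needs 480 per arm. Allowing 5% dropout gives 504 (480 x 1.05) or 506 (480/0.95), against 505 stated.
- Expected events: 505 x 0.10 + 1010 x 0.04 = 90.9, against about 90 stated.
- With 380 evaluable per arm (400 less 5%) and 2-sided 0.05, power is 87.4%, against about 87% stated.

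**Assumptions.** There is no true effect on non-RSV illness. The values of c and u, and the non-RSV risk, are not in the documents and are shown as ranges. The 10% and 4% are first treated as true RSV rates.

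**Exclusion alone.** Let a be the non-RSV risk in infants who would not have an RSV event on placebo. The numerator share is 0.9a on placebo and 0.9a + 0.06c on REGN2222, because treatment spares 6% of infants the RSV event and so keeps them eligible. The difference is +0.06c.

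- With a = c = 20%: 18.0% against 19.2%, or +1.2 points. The standard error is sqrt[(0.18 x 0.82 + 0.192 x 0.808)/400] = 2.75 points, so this is 0.44 SE.
- With a = c at 5, 10, 20, 30 and 40%: +0.3, +0.6, +1.2, +1.8 and +2.4 points, or 0.2 to 0.7 SE.
- If infants prone to RSV are twice as likely to have another illness: +0.5 to +4.4 points over the same overall risks, or 0.4 to 1.3 SE. It exceeds 1 SE only at risks of 30% or more. At 40% the shares are 32.7% and 37.1%, SE 3.37.

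**Both rules together.** Untested RSV illness adds 0.10u on placebo and 0.04u on REGN2222. The net difference is 0.06c - 0.06u = 0.06 x (c - u), in points:

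| c | u = 0 | u = 5% | u = 10% | u = 20% | u = 30% |
|---|---|---|---|---|---|
| 5% | +0.3 | 0.0 | -0.3 | -0.9 | -1.5 |
| 10% | +0.6 | +0.3 | 0.0 | -0.6 | -1.2 |
| 20% | +1.2 | +0.9 | +0.6 | 0.0 | -0.6 |
| 30% | +1.8 | +1.5 | +1.2 | +0.6 | 0.0 |
| 40% | +2.4 | +2.1 | +1.8 | +1.2 | +0.6 |

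The sign changes at u = c. A simulation of 3 million infants per arm agreed with the formula to within 0.1 point at the settings tried.

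**If 10% and 4% are confirmed rates.** True RSV rates are then higher by 1/(1 - u), and the net is 0.06 x (c - u)/(1 - u). At c = 20% and u = 30% this is -0.86 rather than -0.6. The sign change stays at u = c. The extreme of the grid (c = 5%, u = 30%) becomes -2.14 points, from 8.57% against 6.43%. Its SE is sqrt[(0.0857 x 0.9143 + 0.0643 x 0.9357)/400] = 1.86 points, so this corner reaches 1.15 SE.

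**Can other planned outputs recover the answer?** Adding this proportion to the observed-case primary proportion (SAP 5.7.1.3) approximates all-cause hospitalization or outpatient LRTI. At 20% non-RSV risk with independence and u = 0, that is 18.0 + 10.0 = 28.0% against 19.2 + 4.0 = 23.2%, a fall of 4.8 points. A true non-RSV excess of 1.2 points with no overlap gives the same 6.0 - 1.2 = 4.8, so this sum cannot separate artefact from effect.

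**The case against.** The best case for leaving the plan alone has several parts.

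- **Materiality.** The analysis is exploratory, has no test or decision rule, and the bias is usually below one standard error. It vanishes if c = u. This stands, and it sets the weight of the point.
- **Testing may be nearly complete.** The local RT-PCR fallback in SAP 4.6.1 shrinks the untested group, and SAP 5.11 reports how many subjects were swabbed. This stands. It makes u small but leaves the exclusion bias unopposed.
- **Other outputs help.** SAP 4.6.3 item 9 minus item 4 gives hospital visits not confirmed as RSV, with no exclusion of infants who had an RSV event. Item 14 counts respiratory visits after the first RSV episode and so bears on overlap. These are partial checks: they count visits rather than subjects, untested illness stays in the remainder, and the outpatient counts mix upper and lower tract illness.
- **The added row is not unbiased either.** If a share f of RSV illnesses is followed by a late negative swab under a separate AE, that row is off by -0.06 x f x (1 - c) when u = 0. At c = 20% this is -0.24, -0.48 and -0.96 points for f = 5, 10 and 20%. In some settings it is further from zero than the current row: with c = u = 20% and f = 10%, -0.4 against 0.0. With c = 20%, u = f = 10% and 5% of RSV illnesses swab-negative outright, it is -0.7 against +0.3. This stands too. The gain is that the direction of this error is known, and it is limited because any positive test labels the whole episode RSV.

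A reader might also infer three stronger things. One is that the denominator is undefined, but SAP 3.1 supplies the FAS. Another is that the pathogen table in SAP 5.12 inherits the exclusion. In 5.7.5.3, however, the exclusion is worded as a rule for computing that proportion rather than as part of the illness definition, so the text does not establish this. The third is that the analysis is tilted in one known direction. That would need values of c and u, which the documents do not give.

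**Conclusion.** The point holds as a minor one. As written, the contrast in SAP 5.7.5.3 is not a clean estimate of the effect on non-RSV illness, because both numerator rules depend on an outcome that treatment changes. With no true effect, the expected difference is about 0.06 x (c - u). The difference itself will be observed; what cannot be known in advance is the direction of the net bias within it. If testing is nearly complete, u is probably below c and the bias makes REGN2222 look worse.

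Over the ranges in the table, which are assumptions, the bias is -1.5 to +2.4 points. It is larger only if RSV-prone infants are also more prone to other illness, or if untested RSV is frequent and the design rates are read as confirmed rates. No planned output removes it, and it has no bearing on the primary or secondary efficacy analyses.

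**What to change.** In SAP 5.7.5.3:

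- Add a row counting all FAS subjects with at least one separately recorded MARI episode (hospitalization or outpatient LRTI) whose valid RSV results are all negative, whether or not the infant had an RSV event in another episode.
- Report illnesses with no valid RSV result separately, as 'RSV status unknown'.
- Keep the current row for comparison, labelled 'non-RSV or untested MARI only, no RSV event'.
- Note beside the new row that a late-negative RSV illness recorded as a separate AE may still be counted, a small bias toward fewer on REGN2222.

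A tested-only row that keeps the exclusion is not needed. It leaves +0.06 x c x (1 - u), which at c = 20% and u = 10% is +1.1 points against +0.6 for the current row.

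In SAP 5.12, confirm that the exclusion does not carry over. The pathogen table requires a positive panel result, so untested illnesses largely drop out there and would not offset it.

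The cost is a few SAP sentences and one or two table rows. RSV results are already linked to each illness through the AE record, so nothing new is collected.

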5.8. Analysis of Safety Data

Safety and tolerability will be descriptively summarized, including AEs, clinical laboratory variables, physical exam, and vital signs for the SAF. The summary of safety results will be presented for the treatment groups of combined REGN2222 dose arms with the intent to maximize efforts to detect potential safety signals. The individual REGN2222 dose arms will also be presented with the intent to support the combined regimens. No formal inferential testing will be performed. Summaries will be descriptive in nature.

All safety analyses will be performed, unless otherwise specified, using the following common rules:

- The baseline value is defined as the last available value obtained up to the date and time of the first dose of study drug, unless otherwise specified.
- For clinical laboratory, physical exam, and vital signs variables, all measurements, scheduled or unscheduled, will be assigned to analysis windows defined in Appendix 11.3 in order to provide an assessment for Visit 3 to Visit 7 time points.
- For continuous safety parameters including central laboratory measurements and vital sign scores, descriptive statistics will be used to summarize results and change from baseline values by visit.
- A treatment-emergent Potential Clinically Significant abnormal value (PCSV) is a laboratory value or vital sign that was: normal at baseline but abnormal after treatment with study drug during the TEAE period, or: abnormal at baseline and worsened after treatment with study drug during the TEAE period. Thresholds for treatment-emergent PCSV in laboratory variables and vital signs are defined in Appendix 11.4. Treatment-emergent PCSV criteria will determine which subjects had at least 1 treatment-emergent PCSV, taking into account all assessments including unscheduled assessments. Subjects who had post-baseline PCSV during the TEAE period but missing baseline value will be regarded as having treatment-emergent PCSV. There are no universally accepted normal ranges for preterm infants. The ranges used to determine PCSV criteria are associated with full-term infants (except

for bilirubin) and consequently, the TEPCSV results are to be interpreted with caution.

The summary of safety results will be presented by treatment group (REGN2222 1 dose, REGN2222 2 doses, REGN2222 combined, and placebo).

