### 6.3.3.4. Abnormal Laboratory Values and Laboratory Adverse Events

All laboratory values must be reviewed by the investigator or authorized designee.

Significantly abnormal tests must be repeated to confirm the nature and degree of the abnormality. When necessary, appropriate ancillary investigations should be initiated. If the abnormality fails to resolve or cannot be explained by events or conditions unrelated to the study medication or its administration, the medical monitor must be consulted.

The clinical significance of an abnormal test value, within the context of the disease under study, must be determined by the investigator.

Criteria for reporting laboratory values as an AE are provided in Section 7.2.6.

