#### 9.8.4. Unscheduled Assessments

Extra assessments (laboratory data or vital signs associated with nonprotocol clinical visits or obtained in the course of investigating or managing AEs) will be included in listings, but not summarized by study visit. If more than 1 laboratory value is available for a given visit, the first observation will be used in summaries and all observations will be presented in listings.

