5.8.3. Clinical Laboratory Measurements

Central laboratory measures for chemistry and hematology parameters will be explored through two methods:

First, summaries will focus on study population changes with the intent of identifying deviations on a large scale across time. This approach for continuous variables summarizes both the actual results (at both baseline and post-baseline) and the change from baseline results at each post-baseline scheduled visit. Descriptive statistics include number of subjects, mean, median,

standard deviation, minimum, Q1, Q3, and maximum values for each of the 5 blood collection schedule group (Schedule I through M) by treatment group.

Second, shift tables based on baseline categories of low/normal/high/total will be provided for each post-baseline visit by treatment group. In addition, line plots of change from baseline in lab values over time will be presented with visit plotted on the x-axis and lab values on the y-axis, with treatment group side by side at each time point. In addition to the shift analyses, number (and percentage) of subjects with lab values meeting the treatment-emergent PCSV criteria at least once during the TEAE period will be summarized. These laboratory parameters will be presented by the biological functions defined in Section 4.7.3. Subject listings of laboratory measurements that meet treatment-emergent PCSV criteria will be provided.

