6.4. Visit Windows

Visit windows will be programmatically imposed on those safety measures repeatedly collected over the course of the study. These visit windows are derived from the number of days in study, specifically assigning day ranges to mimic the study assessment schedule provided in the protocol. Data analyzed by time point (including laboratory safety data, vital signs, physical exam) will be summarized using the analysis windows given in Appendix 11.3. These analysis windows will be applicable for the aforementioned safety analyses, and they are defined to provide more homogeneous data for time point-specific analyses. If multiple valid values of a variable exist within an analysis window, the nearest from the targeted study day will be selected. If the difference is a tie, the value after the targeted study day will be used. If multiple valid values of a variable exist within the same day, then the first value of the day will be selected when time is available, or the scheduled visit will be selected.

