6.5. Unscheduled Assessments

For safety laboratory data, vital signs, and physical exams, unscheduled visit measurements may be used to provide a measurement for a time point, a baseline, a last, or a worst value, if appropriate according to their definitions. The measurements may also be used to determine abnormal values and treatment-emergent PCSVs.

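### The SAP windows unscheduled laboratory and vital-sign values into by-visit summaries against Protocol 9.8.4, mainly affecting interim laboratory displays, and splits screening and Day 150 laboratory statistics by sampling schedule

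*SAP*

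**What the plan says.** **Protocol.** Section 9.8.4 defines extra assessments as "laboratory data or vital signs associated with nonprotocol clinical visits or obtained in the course of investigating or managing AEs". These "will be included in listings, but not summarized by study visit". It adds: "If more than 1 laboratory value is available for a given visit, the first observation will be used in summaries". Section 9.8.3 shows out-of-window assessments under the visit recorded on the CRF.

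**SAP.** Section 5.8 covers laboratory, vital-sign and physical-examination variables: "all measurements, scheduled or unscheduled, will be assigned to analysis windows defined in Appendix 11.3", to supply Visits 3 to 7. Section 6.5 confirms that "unscheduled visit measurements may be used to provide a measurement for a time point, a baseline, a last, or a worst value". Where a window holds several values, section 6.4 says "the nearest from the targeted study day will be selected". A tie goes to the later value, and scheduled values on other days get no preference. Section 1.2.3, which should list changes from the protocol's statistical section, declares none.

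**Laboratory tables.** SAP 5.8.3 gives descriptive statistics as "values for each of the 5 blood collection schedule group (Schedule I through M) by treatment group". The shift tables are by visit and treatment group, and the line plots show treatment groups side by side at each visit. Neither mentions a schedule split.

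**Sampling plan (Protocol Table 2, SAP 11.2).** All five schedules have a screening draw and a Day 150/ET draw. Schedules M, L, K and J each add one interim draw, at Days 29, 57, 85 and 113 respectively. Schedule I has no interim draw.

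**The concern.** Unscheduled values are not a random sample of infants. Protocol 6.3.3.4 says "Significantly abnormal tests must be repeated to confirm the nature and degree of the abnormality", and Protocol 6.2.4 and Table 4 provide unscheduled visits for abnormal results, adverse events and suspected hypersensitivity. The protocol keeps such values in listings. The SAP lets them stand as visit values without saying that the rule has changed.

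Two things are at stake. First, interim laboratory displays could combine planned values with values taken because something had gone wrong, and the mix could differ between arms. Second, the laboratory time points with planned draws from every infant are tabulated in fifths, which makes the descriptive comparison between arms less precise than the data allow. SAP 5.8 says that the aim of combining the REGN2222 arms is to improve detection of safety signals, and the split works against that aim.

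**Working it through.** The documents state no figure for this point, so there is none to reproduce.

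**1. The rules side by side**

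- Extra values in by-visit summaries: no under Protocol 9.8.4, yes under SAP 5.8 and 6.5.
- Choice among several laboratory values: the first under Protocol 9.8.4, the nearest to target under SAP 6.4. For example, take a planned Visit 5 draw on Day 80 and a repeat on Day 84. The distances from Day 85 are 5 and 1, so the SAP takes the repeat and the protocol takes the planned value.
- Out-of-window values: by CRF visit under Protocol 9.8.3, by analysis window under SAP 6.4 and 11.3. The Visit 3 window is Days 15 to 42, against a protocol window of Day 29±2.

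**2. Cell sizes**

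Inputs are about 1200 treated (SAP 2.2), 1:1:1 allocation, five schedules and 5% dropout (SAP 2.2). Equal allocation to schedules is assumed, because the documents do not state the ratio.

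- Per arm: 1200/3 = 400. Per schedule and arm: 400/5 = 80.
- Planned interim draws at each of Visits 3 to 6: about 80 per arm. Off-schedule infants: 400 − 80 = 320 per arm.
- Day 150: 0.95 × 400 = 380 per arm pooled, or 0.95 × 80 = 76 per schedule.
- Standard-error ratio, split to pooled: √(380/76) = √(400/80) = √5 ≈ 2.24.

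**3. Possible shift in an unsplit interim mean**

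Let r be the share of the 320 off-schedule infants with an extra draw in a window, and d their average excess in SD. Neither is in the documents, so both are assumed and shown as a range. The shift is d × 320r/(80 + 320r).

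- r = 1%: 3.2 draws, 3.8% of values; shift 0.02 SD (d = 0.5) to 0.08 SD (d = 2).
- r = 2%: 6.4 draws, 7.4% of values; shift 0.04 to 0.15 SD.
- r = 5%: 16 draws, 16.7% of values; shift 0.08 to 0.33 SD.

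This applies to displays without the schedule split. In the split descriptive table, the same draws fall in the four off-schedule cells, at 80r = 0.8, 1.6 or 4 values per cell.

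**4. Vital signs**

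Every infant has a planned value at each of Visits 3 to 7 (SAP 4.7.4). Suppose an unscheduled value on another day exists in the window, and both days are spread evenly over their windows (assumed). Counting day pairs under the SAP 6.4 rule, it displaces the planned value about 7% of the time at Visits 3 and 4, and 16% to 19% of the time at Visits 5 to 7. The planned value usually wins.

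**The case against.** The case on the other side is substantial, and most of it limits the point.

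- **Exposure is limited.** Respiratory-illness visits include no blood draw or vital signs (Protocol Table 3). Table 4 requires extra tests only for suspected hypersensitivity, and these are blood count, liver function and antidrug antibody. SAP laboratory summaries use central-laboratory values, so local hospital results do not enter. This stands, and it is one reason the size cannot be fixed.
- **Off-schedule cells.** A reader might infer that they contain only draws prompted by a problem. The documents do not support that. Every schedule has a planned early-termination draw, and one taken on Days 15 to 42 is windowed to Visit 3. Out-of-window draws can land there too, and Protocol 6.2.4 allows unscheduled visits for any reason that is warranted.
- **A shifted table mean.** A reader might infer that the tabulated interim means are biased by a definite amount. SAP 5.8.3 splits that table by schedule, so off-schedule draws barely touch the planned cell. The mixing is in the shift tables and line plots.
- **Lost Day 150 precision.** A reader might infer that precision is lost throughout. Shift tables, line plots and counts of potentially clinically significant values (PCSV) appear pooled, and no formal testing is planned. At Visits 3 to 6 the split does not shrink the planned cell.
- **Physical examinations.** Protocol 9.8.4 names only laboratory data and vital signs.
- **The SAP may adapt.** Protocol section 9 allows revision for amendments and unexpected issues. That would cover a stated change, but SAP 1.2.3 says that there is none.

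Counting unscheduled values toward treatment-emergent PCSV is a separate and proper use that Protocol 9.8.4 does not bar.

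**Conclusion.** The contradiction between Protocol 9.8.4 and SAP 5.8, 6.4 and 6.5 is in the text and is undeclared. Its practical effect is mainly on interim laboratory displays. The by-visit shift tables and line plots mix planned and selected values, and off-schedule cells of the descriptive table hold only unscheduled, out-of-window or early-termination draws. The illustrative range of 0.02 to 0.33 SD rests wholly on assumed draw rates and excesses, and should not be read as an estimate. The effect on vital signs is small.

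The schedule split is a separate presentation weakness at screening and Day 150/ET. The factor of 2.24 in the standard error holds for the descriptive table only, and assumes equal allocation to schedules.

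All of this concerns descriptive safety displays. Severity is minor.

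**What to change.** 1. In by-visit laboratory and vital-sign summaries, shift tables and line plots, use planned values only, as Protocol 9.8.4 states.
2. Keep unscheduled values for listings and for treatment-emergent PCSV.
3. Pool Schedules I to M in the descriptive laboratory tables at screening and Day 150/ET. At Visits 3 to 6, show the infants planned for a draw at that visit.
4. Align the rules for multiple values and out-of-window values with Protocol 9.8.3 and 9.8.4, or record any remaining departure, with a reason, in SAP 1.2.3.

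The cost is SAP wording and table shells, before database lock. One small downside is that an unscheduled value no longer fills in for a missed planned one.
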